11.1.4.1 AEs

The summary of treatment-emergent adverse events (TEAEs) will include the number and percentage of subjects with at least 1 TEAE by MedDRA System Organ Class and Preferred Term and by placebo, each TAK-510 dose level (Parts 1 and 2 only)/dose regimen (Part 3), and TAK-510 overall within each part of the study separately. Similar summary analyses will be provided for treatment-related TEAEs, SAEs, AESIs, and AEs leading to permanent treatment discontinuation as well. For Part 3 only, similar summary analyses of TEAEs will be performed for the single dose after 7 days of washout from multiple dose regimens of TAK-510 by placebo, TAK-510 single dose level after washout, and TAK-510 single dose overall after washout.

11.1.4.2 Clinical Laboratory Evaluations

Clinical laboratory parameters will be summarized using descriptive statistics for baseline, postdose, and change from baseline to postdose by placebo, each TAK-510 dose level (Parts 1 and 2 only)/dose regimen (Part 3 only), and TAK-510 overall within each part of the study separately. The number and percentage of subjects with at least 1 postdose value meeting the sponsor's markedly abnormal criteria for clinical laboratory parameters will be presented by placebo, each TAK-510 dose level (Parts 1 and 2 only)/dose regimen (Part 3 only), and TAK-510 overall within each part of the study separately. For Part 3 only, similar summary analyses of clinical laboratory data will be performed for the single dose after 7 days of washout from multiple dose regimens of TAK-510 by placebo, TAK-510 single dose level after washout, and TAK-510 single dose overall after washout.

11.1.4.3 Vital Signs

Typically, BP and pulse assessments are made in duplicate with an interval of approximately 2 minutes between the 2 assessments. The investigator can take a third BP and pulse assessment if

results are inconsistent (as defined in Section 9.2.4). If the assessments are made in duplicate, the average value of the duplicate assessments will be used in the summary analysis. If the investigator takes a third BP and pulse assessment when results are inconsistent, the average value of the 2 more consistent corresponding assessments (details will be provided in the statistical analysis plan) will be used in the summary analysis.

Vital signs (including but not limited to BP) data will be summarized using descriptive statistics for baseline, postdose, and change from baseline to postdose by placebo, each TAK-510 dose level (Parts 1 and 2 only)/dose regimen (Part 3 only), and TAK-510 overall within each part of the study separately. The number and percentage of subjects with at least 1 postdose value meeting the sponsor's markedly abnormal criteria for vital signs (including by not limited to BP) will be presented by placebo, each TAK-510 dose level (Parts 1 and 2 only)/dose regimen (Part 3 only), and TAK-510 overall within each part of the study separately. For Part 3 only, similar summary analyses of vital signs data will be performed for the single dose after 7 days of washout from multiple dose regimens of TAK-510 by placebo, TAK-510 single dose level after washout, and TAK-510 single dose overall after washout.

All vital sign data will be listed by subject and treatment group for each part of the study.

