Optional DNA samples will also be collected from subjects that provide consent for collection through a separate procedure. DNA samples can be collected at any time on the day of discharge (Day 8) or at early termination (if applicable). Subjects will be discharged on Day 8 and will be readmitted the evening prior to redosing. After a 7-day washout (168 hours after the last dose of the 7-day treatment period), subjects will be dosed with a single dose of study drug (ie, at the same dose and double-blind treatment assignment as their highest daily dose during the 7-day treatment period). The duration of washout may be subject to change based on emerging safety, tolerability, and available PK data. Subjects will be confined the evening prior to redosing and for at least 30 hours after their redosing, while not being confined for the entire washout period. Subjects will return after discharge for additional immunogenicity and other assessments at follow-up visits on Day 29. Based on emerging safety, tolerability, and available PK data, subjects may be confined during washout at the discretion of the investigator in consultation with the sponsor and medical monitor.

In Part 3, up to 3 cohorts may be dosed sequentially for 7 days using a dose titration design of 1 to 5 days at lower doses followed by 2 to 6 days at the highest dose for that cohort, which will not exceed the dose studied in the highest completed dose cohort in Part 2. Cohorts 18 and 19 may be started in parallel. The proposed dose titration designs for the 3 cohorts are as follows:

Cohort 18: Single doses that escalate on a daily basis will be given on the first 2 to 5 days of the 7-day dosing period, followed by a maximum daily dose on the remaining days of the 7-day dosing period.

Cohort 19: A lower starting dose will be given on the first 2 to 3 days of the 7-day dosing period, followed by a maximum daily dose for the remaining days of the 7-day dosing period. The lower starting dose is to be determined based on Cohort 18.

Cohort 20: The initial daily dose(s) are to be determined by Cohorts 18 and 19 and will be given on the first 1 to 3 days, followed by the maximum daily dose for the remaining days of the 7-day dosing period. The maximum daily dose will be the same as that Cohorts 18 and 19, or higher as supported by safety, tolerability, and PK data from at least the same daily dose (or higher) in Part 2 MRD cohorts.

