6.2 Stopping Rules

6.2.1 Stopping Criteria for Individual Subjects

Subjects will permanently discontinue study drug for any study drug-related adverse events that are rated Grade ≥ 3 in severity on the National Cancer Institute (NCI) Common Terminology Criteria for Adverse Events (CTCAE) scale (v5.0).

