6.3 Rationale for Study Design, Dose, and Endpoints

6.3.1 Rationale of Study Design

A randomized, double-blind, placebo-controlled design for Part 1 is considered adequate to characterize the safety, tolerability, and PK of single doses of TAK-510.

Part 2 of the study is a randomized, double-blind, placebo-controlled, sequential panel MRD study where up to 8 cohorts may be studied under repeat-dose conditions.

The intention with the dose titration part of Part 3 is to provide an exploratory evaluation to assess the safety and tolerability profile of dose titration at the start of the 7-day treatment period. This comparison will be descriptive (ie, without hypothesis testing) versus tolerability findings in Parts 1 and 2 with comparable exposures to determine whether dose titration results in different tolerability. The redosing part of Part 3 is intended to provide an exploratory evaluation to assess the effects of a single dose (after 7 days [168 hours] of washout following the 7-day treatment period) on vital signs, adverse events, and other safety parameters.

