6.3.2.5 Rationale for Dose Titration and Redosing After Washout

Part 3 of the study is intended to evaluate whether dose titration can result in a different tolerability, particularly with regard to cardiovascular effects, and whether redosing after a 7-day washout results in cardiovascular effects (ie, loss of potential attenuation of cardiovascular effects with dose titration and multiple dosing). GLP-compliant and non-GLP-compliant cardiovascular safety studies in telemetered dogs with TAK-510 have demonstrated: (1) a dose-response of cardiovascular effects, where the lowest dose tested [REDACTED] results in an ~ED₅₀ (median effective dose) of maximal heart rate and blood pressure effects observed in dogs; (2) repeat-dosing at therapeutic doses results in a significant attenuation of cardiovascular effects following administration of the second daily dose. These data demonstrate that sub-therapeutic

doses can elicit minimal cardiovascular effects and that repeat dosing may elicit tachyphylaxis. Thus, Part 3 of this study is designed to test these concepts clinically to identify the appropriate tolerizing doses, escalation, and length of time of exposure that can potentially minimize cardiovascular effects at therapeutic doses.

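### Part 3 rechallenges each subject at their own highest dose to see whether cardiovascular attenuation is lost, but the vital-sign analysis names no same-subject contrast between the two periods

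*Protocol*

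**What the plan says.** Protocol Section 6.3.2.5 says that Part 3 should evaluate "whether redosing after a 7-day washout results in cardiovascular effects (ie, loss of potential attenuation of cardiovascular effects with dose titration and multiple dosing". It rests this on telemetered dogs, in which "repeat-dosing at therapeutic doses results in a significant attenuation of cardiovascular effects following administration of the second daily dose", and says that Part 3 is to test these ideas clinically.

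Section 6.1.4 sets the redose "at the same dose and double-blind treatment assignment as their highest daily dose during the 7-day treatment period". The schedules for Day 7 (Table 3.i) and Day 14 (Table 3.j) repeat heart rate and blood pressure at the same nominal times after dosing. Section 7.4.1.2 requires the same fasting on Days 7 and 14 of Part 3, and on Days 1 and 5 of Part 2.

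For the analysis, Section 11.1.4.3 plans descriptive summaries of the values before and after dosing and of the "change from baseline to postdose by placebo, each TAK-510 dose level (Parts 1 and 2 only)/dose regimen (Part 3 only), and TAK-510 overall". For the redose it adds: "For Part 3 only, similar summary analyses of vital signs data will be performed for the single dose after 7 days of washout". Section 11.1.4 has the same structure and excludes formal tests and inference for safety. Listings are also planned: "All vital sign data will be listed by subject and treatment group for each part of the study".

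Section 6.2.1 ends dosing for some subjects: "Subjects will permanently discontinue study drug for any study drug-related adverse events" of Grade 3 or higher. Section 6.1.4 allows drop-outs to be replaced.

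**The concern.** Whether attenuation is lost after washout is a question about change within a person, and the design supplies the pair: same subject, dose, clock times and fasting. The analysis text keeps the two halves apart. A reader of the report would have to subtract one group mean from another, with no standard deviation for the difference and hence no measure of its uncertainty.

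The rows may not even correspond. The multiple-dose period is summarized by regimen and the redose by single dose level, while Section 6.1.4 foresees cohorts with different titration schedules and the same maximum dose.

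At stake is how clearly Part 3 can answer its own rationale with 6 active subjects per cohort. For contrasts that start from an early dosing day, the early and late summaries may also rest on different people.

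**Working it through.** **Inputs from the protocol.** Part 3 has up to 3 cohorts of 8 allocated 3:1: 3 x 8 = 24, as stated, giving 3 x 6 = 18 on TAK-510 and 3 x 2 = 6 on placebo. The protocol gives no standard deviation, correlation, precision target or drop-out rate for vital signs.

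**Assumptions of this review.** SD of the heart-rate change 8 bpm on each day; between-day correlation rho 0.4 to 0.8.

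**Precision.** Standard error (SE) of the difference between two days:
- read as two independent summaries: SD x sqrt(2/n)
- paired: SD x sqrt(2(1-rho)/n), so the ratio is sqrt(1-rho)

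| n | Unpaired SE (bpm) | Paired, rho 0.4 | Paired, rho 0.6 | Paired, rho 0.8 |
|---|---|---|---|---|
| 6 | 4.6 | 3.6 | 2.9 | 2.1 |
| 18 | 2.7 | 2.1 | 1.7 | 1.2 |
| Ratio | 1 | 0.77 | 0.63 | 0.45 |

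Intervals gain less at n=6, because degrees of freedom fall from 10 to 5. The 90% half-width at rho 0.4 goes from 1.812 x 4.62 = 8.4 bpm to 2.015 x 3.58 = 7.2 bpm, a 14% reduction. A paired 95% interval is narrower only if rho exceeds 1 - (2.228/2.571)^2 = 0.25. At rho 0.3 the half-width is 1.24 SD paired against 1.29 SD unpaired.

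**Drop-out, for a contrast that starts from an early day.** Illustration with no true attenuation: mean effect 15 bpm, between-subject SD 8, reading SD 5, and stopping if the first-day effect exceeds 25.
- Total SD = sqrt(64 + 25) = 9.43; cutoff z = 10/9.43 = 1.06; fraction stopping about 14%.
- First-day mean of those who continue, relative to all: -9.43 x 0.2275/0.8554 = -2.51 bpm.
- Later-day group mean minus first-day group mean: -2.51 x rho.
- Completers' paired difference: +2.51 x (1-rho).

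| rho | Group means (bpm) | Completers, paired (bpm) |
|---|---|---|
| 0.4 | -1.0 | +1.5 |
| 0.5 | -1.25 | +1.25 |
| 64/89 = 0.72 | -1.8 | +0.7 |

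The errors have opposite signs. A simulation that removed the strongest first-day responder of 6 agreed: for rho 0.3 to 0.9, group means showed -0.08 to -0.23 SD and completers +0.18 to +0.03 SD. A repeated-measures estimate using all data was about zero, with the correlation taken as known.

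**Which contrasts are exposed.** A subject who stops before Day 7 is missing from both Day 7 and Day 14. Only a stop after the Day 7 dose can distort that contrast. Day 5 minus Day 1 in Part 2 is exposed to any earlier stop.

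**The case against.** The strongest reply is that this belongs to the statistical analysis plan. Section 11.1 leaves analysis variables and methods to that document, and nothing in Section 11.1.4.3 rules out a further table. This stands to the extent that nobody can say, on the protocol alone, that a paired contrast will not be made. But the protocol does fix the form of the redosing analysis, and that form separates the paired periods.

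Second, attenuation is rationale; the formal Part 3 objectives are to characterize safety and tolerability, with no inference. The titration question is between cohorts by design: "This comparison will be descriptive (ie, without hypothesis testing) versus tolerability findings in Parts 1 and 2 with comparable exposures". Both points are right. They limit the consequence to interpretation, and no planned test suffers. A descriptive paired difference is compatible with a plan without tests.

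Third, the listings preserve the pairing and change from baseline is itself within-subject. True, but a listing estimates nothing, and change from baseline does not compare one dosing day with another.

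Three stronger readings are tempting and not supported:
- **Most of the precision is lost.** This depends on a high correlation, and the documents give none.
- **Drop-out will manufacture attenuation and pairing will cure it.** No drop-out rate is given, the trigger used above is not a protocol rule, stops before Day 7 leave the main contrast untouched, and a completers' difference has its own bias.
- **The two periods use different baselines.** Section 11.1.4.3 does not define the baseline for the redose.

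**Conclusion.** The point holds in a limited form. The protocol states a within-subject question, builds a same-dose pair to answer it, and names only separate group summaries for the two halves. Adding the paired difference would multiply the SE by 0.77 to 0.45 if the between-day correlation is 0.4 to 0.8, a range assumed here. With complete data the point estimate does not move. At n=6 the interval gain is modest at the lower end of that range and disappears below a correlation of about 0.25.

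Drop-out is a secondary caution, confined mainly to contrasts that start from an early day. If stopping depends on response, group means and completers' differences err in opposite directions, and above a correlation of 0.5 the completers' error is the smaller in the illustration. Neither display is safe alone.

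**What to change.** Add to Section 11.1.4.3, for semirecumbent and standing heart rate and blood pressure, a descriptive within-subject difference of observed values at matched nominal times:
- **Part 3, main contrast:** redosing day minus last day at the same maximum dose (Day 14 minus Day 7 as scheduled). Define it by role, because the washout may change in Cohorts 19 and 20.
- **Part 2:** Day 5 minus Day 1, where the daily dose is constant.
- **Part 3, secondary:** last minus first day at the maximum dose. It is weaker because the first such day varies by cohort and fasting is not matched on Days 2 to 6.

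Report n, mean, SD and a confidence interval labelled as descriptive, for TAK-510 and for pooled placebo; placebo shows any change due to time or readmission. Differencing observed values needs no baseline rule.

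For contrasts that start from an early day, also show the number contributing on each day and the early-day values of subjects who stopped, and preferably a repeated-measures estimate from all data. Do not present the completers' difference as free of drop-out bias.

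The cost is a few derived variables, about two tables and, if adopted, one simple model. Data collection, conduct and the no-testing policy are unchanged.

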11.1.4.4 ECG

ECG parameters (including but not limited to HR, QT/QTc, PR) will be summarized using descriptive statistics for baseline, postdose, and change from baseline to postdose by placebo, each TAK-510 dose level (Parts 1 and 2 only)/dose regimen (Part 3 only), and TAK-510 overall within each part of the study separately. The number and percentage of subjects with at least 1 postdose value meeting the sponsor's markedly abnormal criteria for ECG parameters (including but not limited to HR, QT/QTc, and increase from baseline in QT/QTc) will be presented by placebo, each TAK-510 dose level (Parts 1 and 2 only)/dose regimen (Part 3 only), and TAK-510 overall within each part of the study separately. For Part 3 only, similar summary analyses of ECG data will be performed for the single dose after 7 days of washout from multiple dose regimens of TAK-510 by placebo, TAK-510 single dose level after washout, and TAK-510 single dose overall after washout.

ECG data will be listed by subject and treatment group for each part of the study.

11.1.4.5 Other Safety Parameters

Physical examination findings will only be presented in the data listings.

11.1.5 Immunogenicity Analysis

Immunogenicity will be summarized using the immunogenicity analysis set. The number and percentage of subjects in each category of the immunogenicity status (ADA-negative or ADA-positive, and low or high ADA titer) will be tabulated by placebo, TAK-510 dose level (Parts 1 and 2 only)/dose regimen (Part 3 only), and TAK-510 overall at scheduled time points within each part of the study separately. The relationship between immunogenicity status (ADA-negative or ADA-positive, and low or high ADA titer) and PK, and safety will be analyzed

if they are applicable. Placebo data will be pooled across cohorts within each part of the study. The same dose level (Parts 1 and 2 only)/dose regimen (Part 3 only) will be pooled across cohorts within each part of the study where appropriate. All data will be provided in by subject listings.

11.1.6 Biomarker Analysis

Biomarker measurements will be summarized using the safety analysis set. The concentrations [REDACTED] at each time point (ie, Day -1 and baseline [predose, Day 1]) will be summarized using descriptive statistics (n, mean, standard deviation, geometric mean, %CV, median, minimum, and maximum) by placebo, TAK-510 dose level (Parts 1 and 2 only)/dose regimen (Part 3 only) within each part of the study separately. In addition, the number and percentage of subjects within each of the 4 categories defined by quartile (ie, 0 to $<Q1$, $Q1$ to $<$ median, median to $<Q3$, $\geq Q3$) of [REDACTED] concentrations will be presented for each time point by placebo, TAK-510 dose level (Parts 1 and 2 only)/dose regimen (Part 3 only) within each part of the study separately. The change from baseline [REDACTED] will be summarized using descriptive statistics (n, mean, standard deviation, median, minimum, and maximum) by placebo, TAK-510 dose level (Parts 1 and 2 only)/dose regimen (Part 3 only), and TAK-510 overall at scheduled time points within each part of the study separately. Placebo data will be pooled across cohorts within each part of the study. The same dose level will be pooled across cohorts within each part of the study where appropriate. All data will be provided in by subject listings.

11.2 Interim Analysis

Safety, tolerability, and available PK data will be reviewed in a blinded manner after completion of each cohort in the dose escalation meeting and before next dose escalation stage in the study (see Section 6.0).

If a data-dependent internal decision is needed to inform the subsequent development of TAK-510 before database lock, an interim analysis may be deemed necessary. The details about situations when such a case occurs and associated interim analyses will be provided in the statistical analysis plan.

11.3 Determination of Sample Size

The selected sample sizes in Parts 1, 2, and 3 of the study are considered sufficient for evaluation of safety and tolerability of TAK-510 in healthy subjects. No formal statistical hypothesis testing is planned in Parts 1, 2, or 3. Therefore, no formal power calculations were performed in the determination of the sample size for this study.

12.0 QUALITY CONTROL AND QUALITY ASSURANCE

12.1 Study-Site Monitoring Visits

Monitoring visits to the study site will be made periodically during the study to ensure that all aspects of the protocol are followed. Source documents will be reviewed for verification of data recorded on the eCRFs. Source documents are defined as original documents, data, and records.

CONFIDENTIAL

The investigator and study site guarantee access to source documents by the sponsor or its designee (CRO) and by the IRB and/or IEC. In the event a monitor cannot visit the site in a timely manner, alternative monitoring approaches, such as remote source verification or telephone contact, may be used to ensure data quality and integrity and maintain patient safety.

All aspects of the study and its documentation will be subject to review by the sponsor or the sponsor's designee (as long as blinding is not jeopardized), including but not limited to the Investigator's Binder, study drug, subject medical records, informed consent documentation, and review of eCRFs and associated source documents. It is important that the investigator and other study personnel are available during the monitoring visits and that sufficient time is devoted to the process.

12.2 Protocol Deviations

The investigator should not deviate from the protocol, except where necessary to eliminate an immediate hazard to study subjects. Should other unexpected circumstances arise that have a deviation from protocol-specified procedures, the investigator should consult with the sponsor or designee (and IRB and/or IEC, as required) for medical and safety assessments.

Significant deviations include, but are not limited to, those that involve fraud or misconduct, increase the health risk to the subject, or confound interpretation of primary study assessment.

12.3 Quality Assurance Audits and Regulatory Agency Inspections

The study site also may be subject to quality assurance audits by the sponsor or designees. In this circumstance, the sponsor-designated auditor will contact the site in advance to arrange an auditing visit. The auditor may ask to visit the facilities where laboratory samples are collected, where the medication is stored and prepared, and any other facility used during the study. In addition, there is the possibility that this study may be inspected by regulatory agencies, including those of foreign governments (eg, the FDA, the United Kingdom Medicines and Healthcare products Regulatory Agency, the Pharmaceuticals and Medical Devices Agency of Japan). If the study site is contacted for an inspection by a regulatory body, the sponsor should be notified immediately. The investigator guarantees access for quality assurance auditors to all study documents as described in Section 12.1.

